5.4.1 Subject Unblinding Procedures

Randomization lists will be maintained by the sponsor. In case of serious adverse events or other medical emergencies that make it necessary to unblind the treatment code for a specific subject, the investigator will, after consultation with the sponsor, submit a written request for unblinding to the Medical Monitor. The request will be documented, and the applicable information will be sent to the investigator via fax or e-mail. Unblinded subjects will be discontinued from the study.

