5.4 Subject Withdrawal or Removal From Study

As stated in the Informed Consent, all subjects reserve the right to withdraw from the study at any time. An effort will be made to determine why a subject discontinues the study prematurely. The reason for study discontinuation will be recorded in the eCRF. All subjects who terminate the study early and have completed the Baseline Visit will be encouraged to complete Week 26/End of Study procedures.

Any subject found to have entered the study in violation of this protocol may be withdrawn from the study after discussion with the sponsor. Any subject who requires the use of an unacceptable concomitant medication may be withdrawn from the study. The investigator will discontinue any subject from the study if, in the investigator's opinion, it is not in the subject's best interest to continue.

If the reason for withdrawal is an AE/ SAE, the specific event will be recorded and every effort will be made by the Investigator to document the outcome. The date that the subject is withdrawn from the study and the reason for discontinuation will be recorded on the Case Report Form. Subjects who discontinue from the study or who are lost to follow up will not be replaced.

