7.3 Stopping Rules

The study is designed as a sequential, overlapping cohort, dose-escalation trial. Enrollment will be halted after each cohort until a safety review has been completed.

- Enrollment will be halted in the event that one serious adverse event (SAE), considered to be probably or definitely related to the administration of study medication, is observed.
- Enrollment will be halted in the event that one AE is observed considered to be indicative of distant spread of study medication or unintended exposure to other beings.
- The Sponsor may stop the study in its entirety or discontinue individual study centers at its discretion for any reason or, e.g. if it is observed that the protocol or sound clinical practices are not being followed, or for any other reasons.

The study protocol calls for only one single application of study medication at Baseline (Week 0). Since there is no continuous treatment, no stopping rules for subjects are

applicable and subjects will be encouraged to participate in the study until the scheduled termination visit at Week 26.

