8.2 Adverse Event Follow-up

Adverse events and Serious Adverse Events will be followed up until their resolution or until a stable outcome has emerged.

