8.2.1 Pregnancy

Every effort must be made to avoid pregnancy during the study. If pregnancy does occur, Eirion Therapeutics must be informed immediately. The mother and fetus must be followed until the birth of the infant. In general, the follow up will include the course, duration, and outcome of the pregnancy, and the infant outcome. As the investigational product is applied only once during the study, subjects having a positive urine pregnancy test at or after the Week 4 Visit will be permitted to remain in the study.

Medically accepted methods of birth control are surgical sterilization (tubal sterilization or hysterectomy), vaginal ring contraceptive, patch contraceptive, injectable contraceptive, implantable contraceptive, Intrauterine Device (IUD), diaphragm, condom, or spermicidal gel or foam. Oral contraceptives (prescribed birth control pill) are also acceptable provided this method has been used for at least 4 months prior to the qualifying visit with no change of the brand within this period.

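### Section 5.4.1 removes every unblinded subject although the only application has been given; this conflicts with section 7.3 and ends the remaining scheduled safety assessments

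*Combined protocol and SAP*

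**What the plan says.** Section 5.4.1 sets the trigger: "In case of serious adverse events or other medical emergencies that make it necessary to unblind the treatment code for a specific subject". The investigator consults the sponsor, submits a written request to the medical monitor and receives the code. The section ends: "Unblinded subjects will be discontinued from the study". It allows no exception and gives no reason.

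Section 7.3 points the other way. It notes that there is one application, at Baseline, concludes that individual stopping rules therefore do not arise, and states its aim for follow-up: "subjects will be encouraged to participate in the study until the scheduled termination visit at Week 26". Section 8.2.1 applies the same reasoning to pregnancy: "As the investigational product is applied only once during the study, subjects having a positive urine pregnancy test at or after the Week 4 Visit" may stay in.

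Several provisions keep data after an early exit:

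- Section 5.4: "All subjects who terminate the study early and have completed the Baseline Visit will be encouraged to complete Week 26/End of Study procedures". Where an AE or SAE is the reason for withdrawal, the investigator is to pursue its outcome.
- Section 3.5: the End of Study column, which also serves early termination, marks haematology, chemistry and anti-botulinum antibodies.
- Section 6.1.9: safety bloods are added to whatever the terminating visit already includes.
- Sections 8 and 8.2: AEs and SAEs "will be followed up until their resolution or until a stable outcome has emerged".

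Section 9.1.2 fills missing post-baseline efficacy scores by LOCF and requires at least one post-baseline visit for the ITT population. Section 5.4 states that subjects who discontinue are not replaced.

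**The concern.** Removal after unblinding usually serves to stop further dosing or to keep unblinded ratings out of the data. With one application already given, the first purpose does not arise. The second concerns the IGA and SSA only; it is no reason to end spread examinations, ECGs or laboratory work.

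The subjects removed are selected by a serious event or an emergency, so their missing data are tied to safety. Section 8 itself warns that subjects may not connect subtle signs of toxin spread with treatment, which is why structured examinations are scheduled. A subject unblinded before Week 4 could reach the cohort safety review (section 3.1) without the examinations that the review expects.

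A site facing a code break also has two instructions, and different sites may follow different ones.

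**Working it through.** The plan states no figure here to reproduce. The check has three parts.

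**1. The sections side by side.**

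| Section | Situation | Reasoning given | Consequence |
|---|---|---|---|
| 5.4.1 | Code broken for an SAE or emergency | None | Subject leaves the study |
| 7.3 | Any subject | One application only | No subject stopping rules; stay to Week 26 encouraged |
| 8.2.1 | Positive pregnancy test at or after Week 4 | One application only | Subject may stay |

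Sections 7.3 and 8.2.1 reason from the single application to continued participation. Section 5.4.1 reaches the opposite result in the same circumstances. Section 8.2 is not part of the conflict, because an event can be followed after a subject has left the scheduled visits.

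**2. What is still outstanding at the code break.** Inputs: post-baseline visits at Weeks 1, 2, 4, 8, 12, 18 and 26 (section 7.2); spread examinations at Weeks 1, 2 and 4 (3.4.2); ECG at Week 2 (3.4.5); laboratory draws at Week 4 and at Week 26/End of Study (3.4.3, 3.4.4). Count the items scheduled after the last visit attended:

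| Last visit attended | Visits (of 7) | Spread examinations (of 3) | ECG (of 1) | Laboratory draws (of 2) |
|---|---|---|---|---|
| Baseline | 7 | 3 | 1 | 2 |
| Week 1 | 6 | 2 | 1 | 2 |
| Week 2 | 5 | 1 | 0 | 2 |
| Week 4 | 4 | 0 | 0 | 1 |
| Week 8 | 3 | 0 | 0 | 1 |

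One laboratory draw and one antibody sample in each row are taken at exit, so they move rather than disappear. If the exit coincides with a scheduled visit, that visit's procedures are done too (6.1.9). Neither the Week 26 column nor the End of Study column of section 3.5 contains a spread examination or an ECG, so an encouraged Week 26 return does not restore those.

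**3. Scale.** One subject is 1/24 = 4.2% of an arm, or 1/36 = 2.8% of a cohort (12 + 24 = 36). The documents give no unblinding rate. For assumed rates r, the expected number is 72r and the chance of at least one is 1 − (1 − r)^72:

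| Assumed r | Expected of 72 | Chance of at least one |
|---|---|---|
| 0.5% | 0.36 | 30% |
| 1% | 0.72 | 52% |
| 2% | 1.44 | 77% |
| 5% | 3.6 | 98% |

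Section 9.1.1 gives no response rates, so power can only be illustrated. The calculation is a normal-approximation comparison of two proportions, two-sided 0.05: Φ[(|p1 − p2| − 1.96·SE0)/SE1], with SE0 the pooled and SE1 the unpooled standard error.

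| Assumed vehicle vs active response | 24 vs 24 | One active subject dropped | Active rate lower by 1/24 |
|---|---|---|---|
| 5% vs 35% | 75.4% | 74.7% | 65.4% |
| 5% vs 45% | 91.9% | 91.3% | 86.4% |
| 10% vs 50% | 88.1% | 87.5% | 81.1% |

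Dropping one subject costs less than one percentage point. The last column shows the effect of an active response rate lower by one subject's worth, as when LOCF records a responder as a non-responder; the cost is 5.5 to 10.0 points. LOCF can also err the other way, by carrying a Week 4 response to Week 26 after the effect has worn off.

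**The case against.** The strongest defence is that the plan already protects most of what matters. Early terminators have laboratory and antibody samples at exit, their events are followed to an outcome, they are encouraged to return at Week 26, and unscheduled safety visits are possible (6.1.10). A reader might infer from section 5.4.1 that safety and outcome data are simply lost, including the final samples. The documents do not support that.

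Nor is every subject with an SAE removed. The trigger is an event that makes unblinding necessary, and emergencies that are not SAEs count as well.

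It can also be said that section 7.3 is a general statement that only encourages attendance, and that section 5.4 lists other grounds for removal, so 7.3 cannot mean that nobody is ever discontinued. That is fair as far as it goes. But those grounds are mostly permissive or rest on the investigator's judgement of the subject's interest. Section 5.4.1 is automatic, gives no ground, and sits against reasoning that the protocol uses twice.

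On dose escalation, a reader might infer that the cohort review would miss the signal. It would not: the event is recorded and reported, and section 7.3 halts enrollment for a single SAE judged probably or definitely related, or a single AE indicating distant spread. What the review may lack is the affected subject's later scheduled examinations.

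The objection with most force concerns the ratings. The code goes to the investigator, who scores the primary IGA. Removal does keep those unblinded scores out of the data, and any change must do the same.

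**Conclusion.** The concern holds in limited form. Section 5.4.1 ends scheduled assessments for every unblinded subject, for no stated reason and against section 7.3. The loss is confined to the spread examinations, the Week 2 ECG and the interim visits not yet held. It is largest for a code break before Week 4; after Week 4, no spread examination or ECG is outstanding.

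The number affected is unknown. Under assumed unblinding rates of 0.5% to 5% it would be about 0.4 to 3.6 subjects of 72, so possibly none. This is not a power problem in the sense of lost sample size. The reasons to act are selective safety follow-up, efficacy data missing because of safety events, and an instruction that sites cannot apply consistently. The point is worth correcting before enrollment, but it does not threaten the trial's main comparison.

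**What to change.** Reconcile section 5.4.1 with section 7.3 so that unblinding alone does not end scheduled data collection, and subjects who consent continue the scheduled safety assessments to Week 26. Withdrawal on the other grounds in section 5.4 is untouched. The change concerns data collection only.

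Flag every IGA and SSA score recorded after the code break. Exclude these scores from the primary analysis and treat those visits under the missing-data rule of section 9.1.2. Add a sensitivity analysis that scores the same visits as non-response. State how a subject unblinded before any post-baseline score enters the ITT analysis, since there is then nothing to carry forward.

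The cost is a wording change, one database flag and one small extra analysis. The primary efficacy handling stays essentially as now, on LOCF; the gain is in safety data and in making any dependence on these subjects visible.

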6 STUDY PROCEDURES

6.1.1 Baseline (Qualifying) Visit

Prior to participating in any aspect of the study, each subject will be fully informed, both verbally and in writing, of the conduct and consequences of the study. Each subject must

sign the written Informed Consent prior to the conduct of the Baseline (Qualifying) evaluation.

The investigator will assign a unique identification code to each subject being evaluated for participation in the trial. The following procedures will be conducted:

- using the rating guide provided in Appendix A, record right and left Investigator's Global Assessment score of Crow's Feet, both, "at rest" and "on contraction"
- using the same rating guide provided in Appendix A, record right and left Subject's Self-Assessment score of Crow's Feet, both, "at rest" and "on contraction"
- record medical history and concomitant diseases
- record concomitant medication usage
- record history of botulinum use
- female subjects of child-bearing potential will be given a urine pregnancy test
- assess eligibility according to the Inclusion and Exclusion criteria in 5.1 and 5.2

If the subject is deemed eligible to participate in the study, the subject will be randomized and treated.

- record vital signs (weight, height, temperature, resting pulse and blood pressure, and respiration rate)
- collect non-fasting blood samples for laboratory safety testing
- record and transmit a 12-lead ECG
- take color photographs (see Appendix C for photograph procedure)
- evaluate for muscle weakness (ocular and the extremities) or difficulty swallowing or breathing (Signs of Botulinum Toxin Spread, Appendix B)
- provide the study medication with the lowest available Kit No. to the investigator.
- apply skin-preconditioning using the Dermalroller
- Investigator will apply the topical treatment to the left and right lateral canthal areas
- record subject's experience with the application process
- evaluate for topical adverse event reactions 30 minutes after application using the Irritation Score in Appendix D
- instruct the subject to avoid sun exposure or tanning beds for two days after treatment
- instruct the subject to avoid strenuous activities on the day of application which will cause them to perspire
- instruct the participant not to touch or let others touch the treatment area until the treatment area is washed with soap and water

- instruct the participant to wash the treatment areas with soap and water no sooner than 12 hours after treatment application but no later than 24 hours after treatment application
- schedule follow-up appointment for the next office visit

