3.4.2 Muscle Weakness or Paralysis

Participants will be monitored for potential signs of *botulinum* induced muscle weakness or paralysis. Subjects will be evaluated for Signs of Botulinum Toxin Spread (muscle weakness - ocular and the extremities) or difficulty swallowing or breathing (cranial nerve assessment, Appendix B).

The neurologic assessments are made at Baseline, Week 1, 2, and Week 4.

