5.2 Exclusion Criteria

- history of adverse reactions to any prior botulinum toxin treatments
- history of vaccination with botulinum toxin
- history of non-response to any prior botulinum toxin treatments
- botulinum toxin treatment in the prior 6 months
- history of periocular surgery, brow lift or related procedures
- soft tissue augmentation or any procedures affecting the lateral canthal region in the prior 12 months
- dermabrasion or laser treatment in the periocular region in the last 6 months
- topical prescription-strength retinoids in the prior 3 months to the treatment area
- application of any topical prescription medication to the treatment area within 14 days prior to treatment
- subjects on clinically significant, concomitant drug therapy (See section 5.3 below).
- present or history of neuromuscular disease, eyelid ptosis, muscle weakness or paralysis
- present or history of “dry eye”
- systemic aminoglycoside use in the week prior to treatment application
- participation in another investigational drug trial or receiving any investigational treatment(s) within 30 days of Baseline
- alcohol or drug abuse within the past 3 years
- female subjects who are pregnant or are nursing a child
- psychiatric disease interfering with the subject’s ability to give informed consent
- refusal or inability to comply with the requirements of the protocol for any reason

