6.1.2 Week 1 Visit (+/- 2 days)

The Week 1 visit will occur one week post Baseline (+/- 2 days):

- ask the open ended “How Do You Feel” question and document answer in the electronic Case Report Form
- if the subject noted any change in well-being since last investigator contact, document details on the Adverse Event eCRF
- record changes in medication usage from the Baseline (Qualifying) visit
- record vital signs (weight, temperature, resting pulse and blood pressure, and respiration rate)
- ask if the subject experienced weakness, lethargy, or difficulty swallowing or breathing
- evaluate for muscle weakness (ocular and the extremities) or difficulty swallowing or breathing (Appendix B)
- using the rating guide provided in Appendix A, record right and left Investigator’s Global Assessment score of Crow’s Feet, both, “at rest” and “on contraction”
- using the same rating guide provided in Appendix A, record right and left Subject’s Self-Assessment score of Crow’s Feet, both, “at rest” and “on contraction”
- take color photographs (see Appendix C for photograph procedure)
- schedule the subject for the next office visit

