8 ADVERSE EVENT REPORTING

Adverse event reporting will be handled in accordance with the IRB requirements and the requirements of other regulatory authorities that may apply, e.g. the Food and Drug Administration.

Adverse Events reporting will be solicited by non-leading "How Do You Feel" questions. Subtle symptoms of local or systemic spread of toxin effect would be unlikely to be recognized by the subjects as related to treatment. Therefore, study participants will be asked if they experienced weakness, lethargy, or difficulty swallowing or breathing. In addition, information derived from change in concomitant medications, laboratory analyses, and clinical observations will be evaluated for possible indications for side effects. Adverse events resulting from concurrent illnesses or reactions to concurrent medications will also be recorded. The Investigator must monitor the condition of the subject throughout the study from the time of obtaining informed consent until the final study visit.

Any adverse event, including both observed and volunteered problems, complaints, and symptoms, will be recorded on the Adverse Event pages of the electronic Case Report Form. When an adverse event occurs, the following information and assessments should be recorded in the adverse event section of the eCRF:

- The signs, symptoms or diagnosis or the event,
- The date and time of onset of the event using the 24-hour clock where midnight is 00:00 and noon is 12:00. Onset is the date when the first sign or symptoms were first noted.
- Date of recovery/ resolution
- The adverse event severity/ intensity using the criteria outlined in Section 8.1.2
- The relationship of the event to the study drug as outlined in Section 8.1.1

- Any other actions required such as therapy, medication, treatment or diagnostic procedure
- Seriousness of the event using the criteria outlined in Section 8.1.3
- Outcome (recovered, recovered with sequelae, not yet recovered, death)

Follow-up of a subject should be conducted until resolution of the adverse event or until the medical condition is stable. The investigator is responsible for the appropriate medical management of all adverse events.

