Appendix B: Signs of Botulinum Toxin Spread

1. Ask the subject to follow the examiner's finger with his or her eyes without moving his or her head. At eye level, the examiner should move his or her finger to the right of the subject's head and then to the left. Repeat this horizontal motion at the level of the subject's forehead and chin. Note whether there is any abnormality in the form of any inability of the subject's eyes to follow the finger.
2. Ask the subject to raise his/her eyelids. Observe any indication for "drooping".
3. Ask the subject to swallow and note any difficulty doing so.
4. Ask the subject to partially flex his or her arms at the elbow, with fist at shoulder level. Ask the subject to attempt to fully flex his or her arms against the resistance of the examiner pulling on the subject's forearms. Note whether there is an abnormality in the form of any muscular weakness.
5. Ask the subject to squat down and stand up again. Watch for any abnormalities or signs of weakness.

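### The targeted toxin-spread symptom question is asked at Weeks 1, 2 and 4 but not before dosing, so lethargy has no targeted baseline and the other symptoms no self-reported one

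*Combined protocol and SAP*

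**What the plan says.** **After dosing.** Sections 6.1.2 to 6.1.4 (Weeks 1, 2 and 4) list two separate tasks. One is a verbal question: "ask if the subject experienced weakness, lethargy, or difficulty swallowing or breathing". The other is the Appendix B examination. Section 8 explains why a direct question is used: subjects would probably not connect subtle symptoms with treatment, so "study participants will be asked if they experienced weakness, lethargy, or difficulty swallowing or breathing".

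**Before dosing.** Section 6.1.1 lists the examination, ahead of the kit, preconditioning and application steps: "evaluate for muscle weakness (ocular and the extremities) or difficulty swallowing or breathing (Signs of Botulinum Toxin Spread, Appendix B". Section 3.4.2 agrees: "The neurologic assessments are made at Baseline, Week 1, 2, and Week 4". The Baseline list contains neither the verbal question nor the open question on how the subject feels, although the schedule in Section 3.5 marks adverse event recording at the screening/baseline visit. The list does include "record medical history and concomitant diseases".

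**Appendix B.** There are five steps: eye movement, eyelids, swallowing ("Ask the subject to swallow and note any difficulty doing so"), arm flexion against resistance, and a squat. No step covers breathing or lethargy.

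**Use of the answers.** Section 9.2.4 bases safety mainly on adverse event frequency. Section 7.3 has a single-event rule: "Enrollment will be halted in the event that one AE is observed considered to be indicative of distant spread of study medication".

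**The concern.** Lethargy and a feeling of weakness are non-specific complaints. When a subject reports one at Week 1, the first thing to settle is whether it was there before the application. The same question asked on Day 0 would give a direct comparison. Without it, the site has the subject's later recollection and whatever the general history happened to pick up.

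The error can go either way: an old complaint recorded as new, or a new symptom put down as long-standing. Two things depend on the answer. One is the adverse event table, with 24 subjects per treatment group. The other is the decision whether a single event indicates distant spread, which can halt enrolment and bears on the safety review before Cohort 2. The study medication is applied once, so a pre-dose answer that was not taken cannot be obtained later.

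**Working it through.** The plan gives no figure on this point, so the main check is to set the four symptoms against what is known before dosing.

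| Symptom in the question | Asked at Weeks 1, 2, 4 | Asked before dosing | Examined before dosing | Other pre-dose information |
|---|---|---|---|---|
| Weakness | Yes | No | Yes (eye movement, eyelids, arms, squat) | Exclusion in Section 5.2: "present or history of neuromuscular disease, eyelid ptosis, muscle weakness or paralysis" |
| Swallowing | Yes | No | Yes (one Appendix B step) | General medical history |
| Breathing | Yes | No | Named in 6.1.1, but no Appendix B step | Respiration rate; general medical history |
| Lethargy | Yes | No | No | General medical history |

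Could the Baseline examination line be read as including the question? The later visits argue against it, because there the question and the examination are listed as separate items and only the examination is listed at Baseline.

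**What can separate old from new under the present text.** Section 8 requires a date and time of onset, and Section 8.1 defines an adverse event as one occurring during use of the study drug. Both help, but for a symptom first elicited at Week 1 the onset is recalled. The wording about a change since the last contact belongs to the open question; the targeted question asks only whether the symptom was experienced. Section 8.1 has no rule for a pre-existing complaint or its worsening.

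**Effect on a rate.** The group size is 24 (Section 3.2). One misclassified subject shifts a group's rate by 1/24 = 4.2 percentage points.

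**Can a false-halt probability be given?** It needs two inputs that the documents lack: p, the share of subjects with one of the four symptoms before dosing, and q, the chance that such a complaint is judged indicative of distant spread. Assume p from 1% to 10% and q from 5% to 100%. A cohort has 12 + 24 = 36 subjects.

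- Chance that a cohort contains at least one such subject: 1 − (1 − p)^36, which is 30% at p = 1%, 52% at 2%, 84% at 5% and 98% at 10%.
- Chance that at least one is also judged to be distant spread: 1 − (1 − pq)^36. At p = 5% this is 8.6% for q = 5%, 16.5% for q = 10%, 36.4% for q = 25% and 84.2% for q = 100%.
- Over the whole assumed range it runs from 1.8% (p = 1%, q = 5%) to 97.7% (p = 10%, q = 100%).

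A range that wide is no estimate. The first set of figures describes who is in the cohort, not how often enrolment would be halted.

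**The case against.** The strongest defence is that much of the baseline already exists. Weakness and swallowing are examined before application, and the same examination is repeated at Weeks 1, 2 and 4, so the signs can be compared like for like. Present or past muscle weakness is an exclusion, and Section 5.1 requires good general health. Medical history is taken before dosing and onset is recorded for every adverse event. The trial is randomised, double-blind and vehicle-controlled, so pre-existing complaints should fall in all groups alike and add noise rather than bias.

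All of that stands, and it limits the point. A reader might infer that an existing complaint is necessarily recorded as a new event, or that one positive answer stops enrolment. The documents support neither. No section turns a positive answer into an adverse event automatically, and Section 7.3 needs a judgement that the event indicates distant spread. Percentages of 52%, 84% or 98% per cohort must likewise not be read as halt risks; that would assume every old complaint is judged to be toxin spread.

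What the defence does not cover is self-report. Lethargy is neither examined nor excluded, and breathing has no examination step. Section 8 itself argues that direct questioning is needed for subtle symptoms, and that argument applies equally to the pre-dose state. Section 3.3 uses static efficacy scores to avoid recall bias, whereas a recalled onset depends on memory. Randomisation protects the comparison between groups, but it does not help in judging a single event in one subject.

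**Conclusion.** The point holds as a modest gap with a cheap remedy. Of the four symptoms asked about after dosing, none has a self-reported baseline. Lethargy has no targeted baseline at all, breathing has only a named item without a defined step plus respiration rate, and weakness and swallowing have an examination baseline.

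The consequence is noise in both directions, in adverse event classification and in the judgement behind the one-event halt. No bias between treatment groups is shown. The finding rests on the visit lists and Appendix B, not on any assumed symptom rate.

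**What to change.** - In Section 6.1.1, before application, add the same question on weakness, lethargy, swallowing and breathing, and record the answer in the eCRF.
- In Section 8, state that later answers are compared with the pre-dose answer when deciding whether a symptom is new or worse.
- Provide both answers to the Cohort 1 safety review.

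The halt rule, sample size, significance level and treatment are unchanged. The cost is about a minute per subject at a visit already taking place, and one eCRF field.
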